9.5.4.4 Expedited Reporting

The sponsor must inform investigators and regulatory authorities of reportable events, in compliance with applicable regulatory requirements, on an expedited basis (ie, within specific time frames). For this reason, it is imperative that sites provide complete SAE information in the manner described above.

9.5.4.5 Breaking the Blind

In the case of a medical emergency where the appropriate treatment of the subject requires knowledge of the study treatment given, the investigator may break the randomization code for an individual subject. In all such cases, the AE necessitating the emergency blind break will be handled as an SAE in accordance with the procedures indicated above. Any broken code will be clearly justified and documented. The medical monitor must be notified immediately of the blind break.

9.5.4.6 Regulatory Reporting of Adverse Events

Adverse events will be reported by the sponsor or a third party acting on behalf of the sponsor to regulatory authorities in compliance with local and regional law and established guidance. The format of these reports will be dictated by the local and regional requirements.

9.5.5 Completion/Discontinuation of Subjects

The investigator may withdraw the subject from the study at any time for safety or administrative reasons. A subject may elect to discontinue the study at any time for any reason. All subjects will continue in the study until the 52-week evaluation is completed. Subjects who discontinue treatment prematurely will be followed up until study completion. All subjects who discontinue the study are to complete the study's early discontinuation procedures indicated in the Schedule of Procedures/Assessments ([Table 2](#)).

The investigator will promptly explain to the subject involved that the study will be discontinued for that subject and provide appropriate medical treatment and other necessary measures for the subject. A subject who has ceased to return for visits will be followed up by mail, phone, or other means to gather information such as the reason for failure to return, the status of treatment compliance, the presence or absence of AEs, and clinical courses of signs and symptoms.

Subjects who discontinue early from the study will be discontinued for 1 of these primary reasons: AE(s), lost to follow-up, subject choice, withdrawal of consent, pregnancy, study terminated by sponsor, or other. In addition to the primary reason, the subject may indicate 1 or more of secondary reasons for discontinuation. Study disposition information will be collected on the Subject Disposition CRF.

Detailed retention strategies will be developed and included in study manual. These include a highly trained and competent staff, easy access to the clinic, reminder and follow-up calls, interactive group sessions with games and hands-on nutrition and physical activity demonstrations, random raffle drawings, social events, birthday and holiday cards, and newsletters. In addition, home visits for assessments of families will be an option, as needed, to maximize data collection. This detailed retention plan will help prevent missing data.

A subject removed from the study for any reason may not be replaced.

9.5.6 Abuse or Diversion of Study Drug

During the study, the investigator will report any concern about abuse or diversion of study drugs by completing the Abuse or Diversion of Study Drug CRF. The DEA Registrant has the responsibility to comply with local, state, and Federal laws to notify the Field Division Office of the DEA of any theft or significant loss of any controlled substances upon discovery of such theft or loss.

9.5.7 Confirmation of Medical Care by Another Physician

The investigator will instruct subjects to inform site personnel when they are planning to receive medical care by another physician. At each visit, the investigator will ask the subject whether he or she has received medical care by another physician since the last visit or is planning to do so in the future. When the subject is going to receive medical care by another physician, the investigator, with the consent of the subject, will inform the other physician that the subject is participating in the clinical study.

9.6 Data Quality Assurance

This study will be organized, performed, and reported in compliance with the protocol, SOPs, working practice documents, and applicable regulations and guidelines. Site audits will be made periodically by the sponsor's or the CRO's qualified compliance auditing team, which is an independent function from the study team responsible for conduct of the study.

9.6.1 Data Collection

Data required by the protocol will be collected on the CRFs and entered into a validated data management system that is compliant with all regulatory requirements. As defined by ICH guidelines, the CRF is a printed, optical, or electronic document designed to record all of the protocol-required information to be reported to the sponsor on each study subject.

Data collection on the CRF must follow the instructions described in the CRF Completion Guidelines. The investigator has ultimate responsibility for the collection and reporting of all clinical data entered on the CRF. The investigator or designee as identified on Form FDA 1572 must sign the completed CRF to attest to its accuracy, authenticity, and completeness.

Completed, original CRFs are the sole property of Eisai and should not be made available in any form to third parties without written permission from Eisai, except for authorized representatives of Eisai or appropriate regulatory authorities.

9.6.2 Clinical Data Management

All software applications used in the collection of data will be properly validated following standard computer system validation that is compliant with all regulatory requirements. All data, both CRF and external data (eg, laboratory data), will be entered into a clinical system.

9.7 Statistical Methods

All statistical analyses will be performed by the sponsor or designee after the study is completed and the database is locked and released for unblinding. Statistical analyses will be performed using WinNonlin and SAS software or other validated statistical software as required. Details of the statistical analyses will be included in a separate statistical analysis plan (SAP).

9.7.1 Statistical and Analytical Plans

The statistical analyses of study data are described in this section. Further details of the analytical plan will be provided in the SAP, which will be finalized before database lock and treatment unblinding.

9.7.1.1 Study Endpoints

9.7.1.1.1 PRIMARY EFFICACY ENDPOINT

- Change in BMI from Baseline to Week 52

9.7.1.1.2 SECONDARY EFFICACY ENDPOINTS

KEY SECONDARY ENDPOINT

- Proportion (%) of subjects achieving at least a 5% BMI reduction at Week 52

OTHER SECONDARY ENDPOINT

- Proportion (%) of subjects achieving at least a 5% BMI reduction at Week 12
- Proportion (%) of subjects achieving at least a 10% BMI reduction at Week 52
- Percentage change in BMI from Baseline to Week 52
- Change and percentage change in BMI from Baseline to Week 52 and proportion (%) of subjects achieving at least a 5% or 10% BMI reduction at Week 52 by the outcome of achieving at least a 5% BMI reduction at Week 12
- Change in waist circumference from Baseline to Week 52
- Change in HbA_{1c} from Baseline to Week 52
- Change in fasting glucose, fasting insulin, and HOMA-IR from Baseline to Week 52
- Change in BP (systolic and diastolic) and heart rate from Baseline to Week 52

- Change in fasting lipid profile (total cholesterol, LDL cholesterol, HDL cholesterol, triglycerides) from Baseline to Week 52
- Proportion (%) of subjects with prehypertension or primary hypertension at Week 52
- Proportion (%) of subjects with dyslipidemia at Week 52

9.7.1.2 Definitions of Analysis Sets

- The Safety Analysis Set is the group of subjects who received at least 1 dose of study drug and had at least 1 postdose safety assessment.
- The Full Analysis Set (FAS) is the group of all randomized subjects regardless of adherence to study drug.
- Per-Protocol Analysis Set (PP) is the group of all randomized subjects who are 80% or greater compliant with study medication, completed the study, have no major protocol deviations, have no violations of inclusion or exclusion criteria, and have BMI data at Baseline and Week 52. The determination of subjects to be excluded from this population based on the above criteria and list of major protocol violations will be included in the SAP and finalized before data base lock.
- The PD Analysis Set is the group of subjects who had sufficient PD data to derive at least 1 PD parameter.
- The PK Analysis Set is the group of all randomized subjects from whom at least 1 valid lorcaserin plasma concentration was obtained with associated documented dosing history.
- The population PK/PD set is the group of randomized subjects with PK information and who have at least 1 adequately documented measurement of BMI.

9.7.1.3 Subject Disposition

The number of subjects screened and the number (percentage) of subjects who failed screening and the reasons for screen failure will be summarized, based on data reported on the CRF.

For study completion, the number (percentage) of treated subjects who completed study treatment and who discontinued from study treatment will be summarized according to the primary reason for discontinuation and also according to secondary reason(s) for discontinuation, based on data reported on the CRF. The number (percentage) will be presented by treatment. The reasons for discontinuation from study treatment will be documented in the CRF and source documentation.

9.7.1.4 Demographic and Other Baseline Characteristics

Demographic and other baseline characteristics for the FAS and Safety Analysis Sets will be summarized for each treatment group using descriptive statistics or frequency count. Continuous demographic and baseline variables include age, height, BMI, waist circumference, and weight; categorical variables include sex and race.

9.7.1.5 Prior and Concomitant Therapy

All investigator terms for medications recorded in the CRF will be coded to an 11-digit character code using the World Health Organization Drug Dictionary. The number (percentage) of subjects who took prior and concomitant medications will be summarized for the Safety Analysis Set by treatment group, Anatomical Therapeutic Chemical class, and World Health Organization Drug Dictionary preferred term (PT). Prior medications will be defined as medications that stopped before the first dose of study drug. Concomitant medications will be defined as medications that started on or after the date of the dosing of study drug and continued up to 30 days afterward.

9.7.1.6 Efficacy Analyses

The FAS will be used as the primary analysis set for all efficacy analyses, while the PP will be used as a supportive analysis. Unless specified otherwise, a 2-sided $\alpha=0.05$ significance level will be used for all efficacy analyses.

Primary Efficacy Analysis

The primary efficacy endpoint is the change in BMI from Baseline to Week 52. The change from baseline in BMI will be analyzed using analysis of covariance model (ANCOVA) with factors of treatment, sex (male and female) as fixed effect, and the baseline age and BMI as covariates. The missing values will be imputed using a pattern mixture model utilizing multiple imputation (MI) assuming the missing values are missing not at random (MNAR). The missing values will be imputed at each visit using all available values including the retrieved measurement from the postdiscontinuation data. The details of the analysis model and missing value imputation method will be further described in the SAP.

In addition, the following analyses will also be considered as sensitivity analyses:

- PP analysis: The same primary efficacy analyses described above will be repeated based on the PP.
- Change from baseline in standardized BMI score (Z-score): The same primary efficacy analyses described above will be repeated using Z-score.

Subgroup analyses and additional sensitivity analyses, if appropriate, may also be performed and will be described in the SAP.

Key Secondary Efficacy Analysis

The key secondary efficacy endpoint is the proportion of subjects achieving at least a 5% BMI reduction at Week 52. The secondary efficacy endpoint will be analyzed only if the test for the primary efficacy endpoint is statistically significant.

The proportion of subjects achieving at least a 5% BMI reduction at Week 52 will be analyzed using a logistic regression model with factors of treatment, and sex (male and female), and baseline BMI as a covariate using FAS. Subjects with any missing assessment at Week 52 will be considered as treatment failures in this analysis.

Other Secondary Efficacy Analyses

Unless specified, for all other secondary efficacy endpoints, the continuous variables will be analyzed using mixed effect model repeated measurement analysis (MMRM) and categorical variables will be analyzed using the Cochran Mantel Haenszel test, Chi-square test, or logistic regression as appropriate. Additional analysis may be performed as needed using appropriate statistical methodologies as specified in SAP.

Subgroup analyses will be performed on the primary efficacy endpoint, including sex (male and female), race (white, black, Asian, and other). Additional subgroups may be explored, if deemed necessary.

No adjustment for multiplicity is planned for other secondary endpoints, subgroup, and sensitivity analyses.

9.7.1.7 Pharmacokinetic, Pharmacodynamic, Pharmacogenomic, and Other Biomarker Analyses

9.7.1.7.1 PHARMACOKINETIC ANALYSES

Lorcaserin plasma concentration-time data will be subjected to population PK analysis using nonlinear mixed effects modeling. The effect of covariates, such as baseline characteristics or demographics, on PK will be explored. Derived exposure parameters such as the maximum observed concentration and the area under the concentration-time curve from time 0 to 24 hours at steady-state will be calculated from the final PK model using individual posterior estimates of the PK parameters and from dosing history. The PK analysis set will be used for this analysis.

9.7.1.7.2 PHARMACODYNAMIC ANALYSES

Change from Baseline in BMI will be assessed as the PD analysis. The PD analysis set will be used for this analysis.

Other assessments (eg, percentage of BMI change, proportion [%] of patients achieving $\geq 5\%$ and $\geq 10\%$ BMI reduction, and change in waist circumference from baseline) will also be assessed as part of the PD analysis. The PK/PD analysis set will be used for this analysis.

9.7.1.7.3 PHARMACOKINETIC/PHARMACODYNAMIC ANALYSES

Population PK/PD modeling will be used to explore the relationship between lorcaserin plasma exposure and response, including but not limited to change in BMI from baseline and the probability of achieving at least a 5% and at least a 10% change in BMI from baseline to Week 52. Additionally, exposure-safety relationships for select safety parameters may be explored graphically, depending on the data at the end of study. Any emergent relationship may be modeled as appropriate. Any parameters based on the study data may be considered for exploratory assessment for its relationship to PK.

9.7.1.7.4 PHARMACOGENOMIC AND PHARMACOGENETIC ANALYSES

Not applicable

9.7.1.8 Safety Analyses

Evaluations of safety will be performed on the Safety Analysis Set. Safety assessments including the incidence of AEs (including changes from baseline in physical examination), growth (CDC growth chart and bone age determined by x-ray of the hand), sexual maturation (Tanner Staging), out-of-normal-range laboratory safety test values, change from baseline in laboratory safety test values, ECGs, and vital sign measurements will be summarized by treatment group using descriptive statistics or frequency count as appropriate. In addition, cognitive function will be evaluated by the WRAML-2, depression will be evaluated by the PHQ-9, and suicidal ideation and behavior will be evaluated by the C-SSRS, and will also be summarized by treatment group using descriptive statistics or frequency count as appropriate. All WRAML-2 raw scores from the Core Battery will be converted to age and gender standard scores for purposes of intra individual comparisons. For echocardiographic assessments, the proportion of subjects who develop FDA-defined valvulopathy, the proportion of subjects who develop pulmonary hypertension [pulmonary hypertension is defined when the subject's systolic pulmonary artery pressure (SPAP) ≥ 40 mmHg evaluated by echocardiograph], and change from baseline in SPAP will be summarized by treatment group at Week 28 and Week 52 using descriptive statistics or frequency count as appropriate.

No hypothesis testing will be performed for the safety assessment.

Study Day 1 for all safety analyses will be defined as the date of the 1st dose of study drug.

9.7.1.8.1 EXTENT OF EXPOSURE

Subjects will receive Belviq XR 20 mg or placebo QD for up to 52 weeks. The extent of exposure will be characterized by duration of exposure (in weeks) for each treatment group.

Duration of exposure will be defined as the number of weeks between the date the subject received the 1st dose of study drug and the date the subject received the last dose of study drug. Duration of exposure will be summarized using descriptive statistics by treatment group. In addition, the duration of exposure will be categorized and will be summarized using frequency count by treatment group.

9.7.1.8.2 ADVERSE EVENTS

The AE verbatim descriptions (investigator terms from the CRF) will be classified into standardized medical terminology using the Medical Dictionary for Regulatory Activities (MedDRA). Adverse events will be coded to the MedDRA (Version 18.0 or higher) lower level term closest to the verbatim term. The linked MedDRA PT and primary system organ class (SOC) are also captured in the database.

A treatment-emergent AE (TEAE) is defined as an AE that emerges during treatment (up to 28 days after the last dose of study drug), having been absent at pretreatment (Baseline) or

- Reemerges during treatment (up to 28 days after the last dose of study drug), having been present at pretreatment (Baseline) but stopped before treatment, or
- Worsens in severity during treatment relative to the pretreatment state, when the AE is continuous.

Only those AEs that were treatment emergent will be included in summary tables. All AEs, treatment emergent or otherwise, will be presented in subject data listings.

The TEAEs will be summarized by treatment group. The following summaries will be reported for TEAES:

- Incidence of TEAEs in descending order of frequency
- Incidence of TEAEs by SOC and PT
- Incidence of treatment-related TEAEs by SOC and PT
- Incidence of TEAEs by SOC, PT and maximum severity (mild, moderate, or severe)
- Incidence of treatment-related TEAEs by SOC, PT, and maximum severity (mild, moderate, or severe)
- Incidence of TEAEs by SOC, PT, and relationship to study drug (Yes [related] or No [not related])

A subject will be counted only once within a SOC or PT, if the subject experienced more than 1 TEAE within a specified SOC and PT.

The following summaries will also be presented for the treatment-emergent SAEs.

- Incidence of TEAEs leading to death
- Incidence of treatment-emergent SAE by SOC and PT
- Incidence of treatment-related treatment-emergent SAE by SOC and PT

In addition, subjects with TEAEs leading to discontinuation from study drug and AEs of special interest as described in Section 9.5.4.3.2 will be summarized by MedDRA SOC and PT for each treatment group.

9.7.1.8.3 LABORATORY VALUES

Laboratory results will be summarized using Système International units, as appropriate. For all quantitative parameters listed in Section 9.5.1.5.3, the actual value and the change from baseline to each postbaseline visit and to the end of treatment (defined as the last on-treatment value) will be summarized by visit and treatment group using descriptive statistics. Percentages will be based on the number of subjects with both nonmissing baseline and relevant postbaseline results.

Laboratory test results will be assigned a low/normal/high (LNH) classification according to whether the value was below (L), within (N), or above (H) the laboratory parameter's reference range. Within-treatment comparisons for each laboratory parameter will be based on 3-by-3 tables (shift tables) that compare the baseline LNH classification to the LNH classification at the End of Treatment and the Follow-Up visits. Similar shift tables will also compare the baseline LNH classification to the LNH classification for the highest and lowest value during the treatment period.

Appendix 1 presents the criteria that will be used to identify subjects with treatment-emergent markedly abnormal laboratory values (TEMAV). Except for phosphate, a TEMAV is defined as a postbaseline value with an increase from baseline to a grade of 2 or higher. For phosphate, a TEMAV was defined as a postbaseline value with an increase from baseline to a grade of 3 or higher. When displaying the incidence of TEMAVs, each subject may be counted once in the laboratory parameter high and in the laboratory parameter low categories, as applicable.

9.7.1.8.4 VITAL SIGNS

Descriptive statistics for vital signs parameters (eg, systolic and diastolic BP, pulse, respiratory rate, temperature, weight) and changes from baseline will be presented by visit and treatment group.

9.7.1.8.5 ELECTROCARDIOGRAMS

For each ECG parameter (including PR interval, RR interval, QRS interval, QT interval, QTc interval (Bazett formula), QTc interval (Fridericia formula), and heart rate), the actual value and change from baseline will be summarized by visit and treatment group using descriptive statistics.

Shift tables will present changes from baseline in ECG interpretation (categorized as normal; abnormal, not clinically significant; and abnormal, clinically significant) to end of treatment.

Maximum postbaseline QTc (Bazett) and QTc (Fridericia) will also be tabulated by treatment group as follows:

- Number (percentage) of subjects in greater than 450 msec, greater than 480 msec, and greater than 500 msec during the treatment, and
- Number (percentage) of subjects with an increment of greater than 30 msec and greater than 60 msec from the baseline visit.

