9.5.1.5.9 ELECTROCARDIOGRAMS

Twelve-lead ECGs will be obtained as designated in the Schedule of Procedures/Assessments ([Table 2](#)).

An ECG abnormality may meet the criteria of an AE as described in this protocol (see [Section 9.5.1.5.1](#)) and the CRF Completion Guidelines. In these instances, the AE corresponding to the ECG abnormality will be recorded on the Adverse Events CRF.

For ECG abnormalities meeting criteria of an SAE (see [Section 9.5.1.5.2](#)), the site must fax or email the SAE report including the ECG report to the sponsor using the SAE form (see [Section 9.5.4.1](#)).

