9.7.1.8.3 LABORATORY VALUES

Laboratory results will be summarized using Système International units, as appropriate. For all quantitative parameters listed in [Section 9.5.1.5.3](#), the actual value and the change from

baseline to each postbaseline visit and to the end of treatment (defined as the last on-treatment value) will be summarized by visit and treatment group using descriptive statistics. Percentages will be based on the number of subjects with both nonmissing baseline and relevant postbaseline results.

Laboratory test results will be assigned a low/normal/high (LNH) classification according to whether the value was below (L), within (N), or above (H) the laboratory parameter's reference range. Within-treatment comparisons for each laboratory parameter will be based on 3-by-3 tables (shift tables) that compare the baseline LNH classification to the LNH classification at the End of Treatment and the Follow-Up visits. Similar shift tables will also compare the baseline LNH classification to the LNH classification for the highest and lowest value during the treatment period.

[Appendix 1](#) presents the criteria that will be used to identify subjects with treatment-emergent markedly abnormal laboratory values (TEMAV). Except for phosphate, a TEMAV is defined as a postbaseline value with an increase from baseline to a grade of 2 or higher. For phosphate, a TEMAV was defined as a postbaseline value with an increase from baseline to a grade of 3 or higher. When displaying the incidence of TEMAVs, each subject may be counted once in the laboratory parameter high and in the laboratory parameter low categories, as applicable.

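### The ECG interpretation shift table stops at end of treatment, so a completer's transient Week 28 abnormality never enters it

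*Protocol*

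**What the plan says.** All references are to protocol v7.0.

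- **Interpretation (9.7.1.8.5).** "Shift tables will present changes from baseline in ECG interpretation (categorized as normal; abnormal, not clinically significant; and abnormal, clinically significant) to end of treatment". No by-visit or worst-value summary of the interpretation is stated.
- **Numeric ECG parameters (9.7.1.8.5).** For the PR, RR, QRS, QT and QTc intervals and heart rate, "the actual value and change from baseline will be summarized by visit and treatment group using descriptive statistics".
- **QTc extremes (9.7.1.8.5).** "Maximum postbaseline QTc (Bazett) and QTc (Fridericia) will also be tabulated by treatment group as follows", followed by threshold and increment categories.
- **Timing (9.5.1.5.9).** "Twelve-lead ECGs will be obtained as designated in the Schedule of Procedures/Assessments". Table 2 marks ECGs at Weeks 0, 28, 52 and 56 and at early discontinuation. It marks none under unscheduled visits.
- **Laboratory values (9.7.1.8.3).** Shift tables go to the "classification at the End of Treatment and the Follow-Up visits". In addition, "Similar shift tables will also compare the baseline LNH classification to the LNH classification for the highest and lowest value during the treatment period". The same section gives the meaning "end of treatment (defined as the last on-treatment value"; section 9.7.1.8.5 uses the term without defining it.

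**The concern.** A safety shift table is usually read as showing how many subjects developed an abnormality on drug. This one shows status at the last assessment. With two scheduled on-treatment ECGs, anything seen at the first and gone by the second drops out of it. The protocol already handles this for laboratory values and QTc by looking at extremes, and section 9.7.1.8.6 summarizes echocardiographic findings at both Week 28 and Week 52. The overall ECG interpretation has no equivalent, although it is the only planned categorical summary that can carry rhythm and morphology findings. At stake is an incomplete count of subjects with a clinically significant on-treatment ECG in an adolescent safety database.

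**Working it through.** The plan states no figure here to reproduce. The check is to trace subjects through the rule and then size the loss under stated assumptions.

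**Tracing subjects, with end of treatment taken as the last on-treatment value**

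| Baseline | Week 28 | Week 52 | Planned shift | Shift to worst on-treatment |
|---|---|---|---|---|
| Normal | Clinically significant | Normal | Normal to normal | Normal to clinically significant |
| Normal | Clinically significant | Clinically significant | Normal to clinically significant | Same |
| Normal | Clinically significant, last on-treatment ECG | None on treatment | Normal to clinically significant | Same |

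Only the first row is misrepresented. A subject who leaves after Week 28 and has an early-discontinuation ECG while still on treatment can lose the Week 28 reading in the same way.

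**Which other outputs catch the first row**

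- QTc outlier: yes, through the maximum postbaseline QTc table.
- Change in PR, QRS or heart rate: possibly. The by-visit summaries include Week 28, but as group descriptive statistics.
- Adverse event: possibly. Section 9.5.1.5.1 makes a defined QTc change an adverse event and leaves other ECG abnormalities to the investigator. Once reported, the event is summarized as treatment-emergent even if it resolves.
- A transient rhythm or morphology finding that is none of these: no stated summary.

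**Meaning of end of treatment.** Table 2 labels the Week 52 visit EOT, and subjects who stop drug are followed to study completion (sections 9.1 and 9.5.5). If the ECG table used the Week 52 visit instead of the last on-treatment value, an early stopper's off-drug ECG would replace the on-drug reading. Either meaning leaves Week 28 out for completers.

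**Size (illustrative).** Let q be the chance of a clinically significant reading at each of two independent on-treatment ECGs. The documents give no value; 2% to 5% is assumed.

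- Shown by the last ECG alone: q.
- Shown by the worst of two: 1 − (1 − q)².
- Share of affected completers missed: q(1 − q) / [1 − (1 − q)²] = (1 − q)/(2 − q).

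| q | Last ECG | Worst of two | Share missed |
|---|---|---|---|
| 2% | 2.0% | 1 − 0.98² = 3.96% | 0.98/1.98 = 49% |
| 3% | 3.0% | 1 − 0.97² = 5.91% | 0.97/1.97 = 49% |
| 5% | 5.0% | 1 − 0.95² = 9.75% | 0.95/1.95 = 49% |

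Taking the 40% dropout in section 9.7.2, completers per arm are 130 × 0.60 = 78. At q = 3% the last ECG shows 78 × 0.03 = 2.3 subjects and the worst of two shows 78 × 0.0591 = 4.6. If every Week 28 finding persists to Week 52, the two tables agree and nothing is lost.

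**The case against.** The best defence is that this is a matter of display. Sections 9.7, 9.7.1 and 9.7.4 leave further detail to the statistical analysis plan, which is not at hand and could add a table. Section 9.7.1.8 says in general terms that ECGs will be summarized by descriptive statistics or counts. ECG and laboratory displays need not match, and the laboratory rule has more to recover: five scheduled on-treatment time points (Weeks 1, 5, 12, 28 and 52) against two. The table does not claim to measure incidence, and section 9.7.1.8 rules out hypothesis testing for safety.

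Much of this stands, and it keeps the point small. It does not remove it. The protocol names the endpoint of this table, so the issue is a stated rule and not silence, and the general sentence names neither a visit nor a worst value.

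A reader might infer more than the documents support:

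- **That a Week 28 abnormality disappears from the report.** It is lost from this table only; the QTc, by-visit and adverse-event routes remain.
- **That conduction findings have no other summary.** PR and QRS are summarized by visit.
- **That laboratory shifts use extremes in place of end of treatment.** They use both, and Follow-Up as well.
- **That the arm comparison is biased because subjects with abnormal ECGs stop drug.** Nothing in the protocol shows this. A worst-value table also depends on who stopped, since early leavers contribute fewer ECGs.

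**Conclusion.** The point holds as a minor improvement. The only stated summary of ECG interpretation omits the Week 28 reading for completers, and a transient finding that is not a QTc outlier, not visible in the interval summaries and not judged an adverse event is summarized nowhere. The loss runs from none, if findings persist, to about half of affected completers, if the two readings are independent with equal rates. The 2% to 5% rates and the independence are assumptions. Independence is not a strict ceiling, because findings concentrated early and then resolving would lose more. No efficacy conclusion or formal safety comparison depends on this table.

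**What to change.** Revise section 9.7.1.8.5 to three effects:

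1. Keep the shift from baseline to end of treatment.
2. Add a shift from baseline to the worst on-treatment interpretation, ordered normal, then abnormal not clinically significant, then abnormal clinically significant. Take it over Week 28, Week 52 or early discontinuation while on treatment, and any other on-treatment ECG actually obtained. Table 2 schedules no unscheduled-visit ECG, so the last part covers only those that happen to be taken.
3. State that end of treatment for ECGs is the last on-treatment value, as section 9.7.1.8.3 already does for laboratory tests.

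The cost is one extra descriptive table from data already collected. The reported rate of clinically significant ECGs may look somewhat less favourable.
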